7.1.3. Population of Interest

The primary PK analyses will be based on the PK concentration population for plasma PK concentrations and the PK parameter population for plasma PK parameters and statistical analysis.

7.1.4. Statistical Analyses / Methods

Details of the planned displays are provided in [Appendix 9: List of Data Displays](#) and will be based on GSK Data Standards and statistical principles.

Unless otherwise specified, endpoints / variables defined in Section [7.1.1](#) will be summarized using descriptive statistics and listed.

Primary plasma PK parameters (AUC[0-∞], AUC[0-t], Cmax, and Tmax) will be estimated for GSK3640254. Summary statistics (arithmetic mean, geometric mean, median, standard deviation (SD), coefficient of variation (CV), minimum, maximum, between-subject coefficient of variation (CVb), and 90% confidence interval (CI) for plasma GSK3640254 PK parameter values will be summarized by treatment.

7.1.4.1. Statistical Methodology Specification

The following PK statistical analyses will only be performed if sufficient data are available (i.e. if participants have well defined plasma profiles).

Endpoint / Variables

 • Plasma primary PK endpoints include AUC(0-∞), AUC(0-t), Cmax, and Tmax for GSK3640254 as data permit
Model Specification

 • Analysis will be performed to compare the relative BA of a tablet formulation of GSK3640254 with the capsule formulation, as appropriate. Analyses will be performed on the natural logarithms of AUC(0-∞), AUC(0-t), and Cmax using linear mixed-effect models with treatment, period, and sequence as fixed effects and participant as a random effect. Effects will be estimated, and CIs will be constructed for the following treatment comparisons: 
 ○ Treatment B (test) versus Treatment A (reference) ○ Point estimates and 90% CIs for treatment differences on the log scale derived from the model will be exponentiated to obtain estimates for geometric mean ratios and CIs on the original scale. • The effect of food (moderate or high fat meal) on the PK of the tablet formulation of GSK3640254 will be similarly analyzed for the following treatment comparisons: 
 ○ Treatment B (test) versus Treatment C (reference) ○ Treatment D (test) versus Treatment C (reference) • Non-parametric analysis will be performed to compare the Tmax of a tablet formulation of GSK3640254 with the capsule formulation, as appropriate. The Hodges-Lehmann estimate will be used to produce the median, median difference, and 90% CIs for the following treatment comparison: 
 ○ Treatment B (test) versus Treatment A (reference) ○ A p-value will be generated by the Wilcoxon signed-rank test • The effect of food (moderate or high fat meal) on the Tmax of the tablet formulation of GSK3640254 will be similarly analyzed for the following treatment comparisons: 
 ○ Treatment B (test) versus Treatment C (reference)

 ○ Treatment D (test) versus Treatment C (reference)
Model Checking & Diagnostics

 ● Model assumptions will be applied, but appropriate adjustments may be made based on the data.
Model Results Presentation

 ● Statistical analysis for comparison of relative BA by analysis of variance (ANOVA) will be presented in tabular format with geometric mean ratios for the following treatment comparison: 
 ○ Treatment B (test) versus Treatment A (reference) ● Statistical analysis for the effect of food (moderate or high fat meal) by ANOVA will be presented in tabular format with geometric mean ratios for the following treatment comparisons: 
 ○ Treatment B (test) versus Treatment C (reference) ○ Treatment D (test) versus Treatment C (reference) ● Statistical analysis for comparison of Tmax of a tablet formulation with a capsule formulation by non-parametric analysis will be presented in tabular format with the median, median difference, and 90% CIs along with a p-value generated by the Wilcoxon signed-rank test for the following treatment comparison: 
 ○ Treatment B (test) versus Treatment A (reference) ● Statistical analysis for comparison of the effect of food (moderate or high fat meal) on the Tmax by non-parametric analysis will be presented in tabular format with the median, median difference, and 90% CIs along with a p-value generated by the Wilcoxon signed-rank test for the following treatment comparisons: 
 ○ Treatment B (test) versus Treatment C (reference) ○ Treatment D (test) versus Treatment C (reference)

7.2. Secondary Pharmacokinetic Analyses

7.2.1. Endpoint / Variables

7.2.1.1. Drug Concentration Measures

Refer to [Appendix 3: Data Display Standards & Handling Conventions \(Section 10.3.3 Reporting Standards for Pharmacokinetic\)](#).

7.2.1.2. Derived Pharmacokinetic Parameters

Pharmacokinetic parameters will be calculated by standard non-compartmental analysis according to current working practices and using the currently supported version of WinNonlin (8.0 or higher). All calculations of non-compartmental parameters will be based on actual sampling times.

CONFIDENTIAL

209713

Plasma pharmacokinetic parameters listed below will be determined from the plasma concentration-time data, as data permits:

Parameter	Parameter Description
t _{lag}	Lag time for absorption
t _{1/2}	Apparent terminal phase half-life
CL/F	Apparent oral clearance
V _z /F	Apparent volume of distribution

NOTES:

- Additional parameters may be included as required.

7.2.2. Summary Measure

Pharmacokinetic parameters t_{lag}, t_{1/2}, CL/F, and V_z/F following single dose administration of GSK3640254 to healthy participants.

7.2.3. Population of Interest

The secondary PK analyses will be based on the PK concentration population for plasma PK concentrations, and the PK parameter population for plasma PK parameters, unless otherwise specified.

7.2.4. Statistical Analyses / Methods

Details of the planned displays are provided in [Appendix 9: List of Data Displays and statistical principles](#).

Unless otherwise specified, endpoints/variables defined in Section [7.2.1](#) will be summarized using descriptive statistics and listed.

Secondary plasma PK parameters (t_{lag}, t_{1/2}, CL/F, and V_z/F) will be estimated for GSK3640254. Summary statistics (arithmetic mean, geometric mean, median, CV, SD, minimum, maximum, CV_b, and 90% CI) for secondary plasma PK parameters of GSK3640254 will be summarized by treatment.

Summary statistics (arithmetic mean, median, standard deviation, minimum, maximum, and coefficient of variation) for plasma GSK3640254 PK concentrations will be summarized by treatment using the PK Concentration Population.

8. SAFETY ANALYSES

The safety analyses will be based on the Safety population unless otherwise specified.

8.1. Adverse Events Analyses

Adverse event analyses including the analysis of AEs, SAEs, and other significant AEs will be based on GSK Core Data Standards. The details of the planned displays are provided in [Appendix 9](#): List of Data Displays.

8.2. Clinical Laboratory Analyses

Laboratory evaluations including the analyses of chemistry laboratory tests, hematology laboratory tests, urinalysis, and liver function tests will be based on GSK Core Data Standards and will be graded using the Division of AIDS (DAIDS) Table for Grading the Severity of Adult and Pediatric Adverse Events (Version 2.1, July 2017). The details of the planned displays are in [Appendix 9](#): List of Data Displays.

8.3. Adverse Events of Special Interest

At the end of the study, QT prolongation, gastrointestinal intolerability/toxicity, psychiatric events, and nervous system disorders will be summarized by treatment. A listing will also be provided accordingly.

QT prolongation AE of special interest will be defined as cardiac disorders system organ class (SOC) plus preferred terms (PTs) using the Medical Dictionary for Regulatory Activities (MedDRA) Standardized MedDRA Query (SMQ) “Torsade de pointes/QT Prolongation” (narrow and broad terms) plus seizure.

Gastrointestinal intolerability/toxicity AEs of special interest will be defined within three narrow sub-SMQs [Gastrointestinal nonspecific symptoms and therapeutic procedures SMQ; Gastrointestinal nonspecific dysfunction SMQ; Gastrointestinal nonspecific inflammation (SMQ)] plus a selection of relevant broad PTs from the Gastrointestinal non-specific symptoms and therapeutic procedures SMQ.

Psychiatric AEs of special interest will be defined within the following:

- Sub-SMQ “Suicide/self-injury” (SMQ) from parent SMQ of “Depression and Suicide/Self Injury”. Only narrow terms from the sub-SMQ selected.
- Sub-SMQ “Depression (excluding suicide and self-injury)” (SMQ) from parent SMQ of “Depression and Suicide/Self Injury”. Only narrow terms from the sub-SMQ selected.
- All preferred terms from high level group term (HLGT) “Manic and Bipolar mood disorders and disturbances” under SOC “Psychiatric disorders”.
- Narrow terms from SMQ “Psychosis and psychotic disorders” selected.
- All preferred terms from HLGT “Anxiety disorders and symptoms”, under SOC 'Psychiatric disorders'.

CONFIDENTIAL

209713

- All preferred terms from HLGT “Sleep Disorders and Disturbances” and HLGT “Sleep disturbances (incl subtypes)”.

Nervous system disorders AEs of special interest will be defined within the following:

- Four HLGTs under Nervous System Disorders SOC: “Headaches”; “Mental impairment disorders”; “Neurological disorders” and “Seizures”

8.4. Other Safety Analyses

The analyses of non-laboratory safety test results including electrocardiograms (ECGs), and vital signs will be based on GSK Core Data Standards, unless otherwise specified. A figure of mean change from baseline in QTc using the Fridericia formula (QTcF) interval along with the 2-sided 95% CI using Student’s t distribution will be presented by treatment and visit. The details of the planned displays are presented in [Appendix 9: List of Data Displays](#).

CONFIDENTIAL

209713

9. REFERENCES

ViiV Healthcare group of companies Document Number 2018N383392_00 (30-AUG-2019): A Randomized, Open-Label, Single Dose, Four-Period Crossover Clinical Trial to Assess the Relative Bioavailability of a Tablet Compared to a Capsule of GSK3640254 and to Assess the Effect of Food on the GSK3640254 Tablet in Healthy Participants.

CONFIDENTIAL

209713

10. APPENDICES**10.1. Appendix 1: Schedule of Activities****10.1.1. Protocol Defined Schedule of Events****Screening Visit**

Procedure	Screening (up to 28 days before Day 1)
Outpatient visit	X
Informed consent	X
Inclusion and exclusion criteria	X
Demography	X
Full physical examination including height and weight ¹	X
Laboratory assessments (hematology, chemistry, urinalysis)	X
12-lead electrocardiogram	X
Vital sign measurements	X
Medication/drug/alcohol history	X
Past and current medical conditions	X
Columbia Suicide Severity Rating Scale	X
Serum pregnancy test	X
Follicle-stimulating hormone (as needed, to confirm postmenopausal status)	X
Drug, alcohol, and cotinine screen	X
Human immunodeficiency virus, hepatitis B and C Screening	X

¹. A full physical examination will include at a minimum, assessments of the skin, cardiovascular, respiratory, gastrointestinal (GI), and neurological systems.

CONFIDENTIAL

209713

Time and Events Table

Procedure	Check-in	Periods 1, 2, and 3				Period 4 only				Notes	
		Day -1	Day 1	Washout			Day 1	Day 2	Days 3-4		Day 5 ⁰
				Day 2	Days 3-5	Days 6-7					
Admit to clinic	X										
Discharge from clinic									X	Discharge from clinic following completion of the last study procedure on Day 5 of Period 4.	
Brief physical examination	X				D7 (Period 2 only)				X	Interim or symptom targeted physical examination will be performed at the discretion of the investigator. See Protocol Section 8.2.1 for description of brief physical examination.	
Vital signs	X	X	X	D3-5		X	X	X	X	Blood pressure and pulse will be measured in triplicate predose on Day 1 in Periods 1-4. Single blood pressure and pulse will be measured predose on other study days.	
12-lead ECG	X	X				X			X	All ECGs on Day 1 in Periods 1-4 will be predose, postdose at 2 hours, and postdose at 4 hours. The predose ECGs in Periods 1-4 will be taken in triplicate.	
Drug, alcohol, and cotinine screen	X									See Protocol Appendix 2 for specific tests to be performed.	
Laboratory assessments (hematology, chemistry, urinalysis)	X		X				X		X	See Protocol Appendix 2 for specific tests to be performed. Day 2 samples in each period to be collected 24 hours after dosing.	
Pregnancy test	X								X	Serum testing at Day -1	

CONFIDENTIAL

209713

Procedure	Check-in	Periods 1, 2, and 3				Period 4 only				Notes	
		Day -1	Day 1	Washout			Day 1	Day 2	Days 3-4		Day 5 ¹
				Day 2	Days 3-5	Days 6-7					
Columbia-Suicide Severity Rating Scale	X				D7				X		
Genetic sample (optional)	X										
Study intervention: GSK3640254 200 mg (capsule or tablet)		X				X				Participants will fast overnight for at least 10 hours prior to dosing; be provided a moderate fat meal, a high fat meal, or no meal 30 minutes prior to dosing; and be provided standardized meals ≥4 hours postdose. See Protocol Section 4.1.	
Serial PK sampling		X	X	X		X	X	X	X	Blood collection for PK analysis of GSK3640254 will be collected within 40 minutes prior to dosing and 1, 1.5, 2, 2.5, 3, 3.5, 4, 4.5, 5, 6, 8, 12, 24, 48, 72, and 96 hours postdose in each period.	
AE review		←-----X-----→									
SAE review		←-----X-----→									
Concomitant medications		←-----X-----→									

AE = adverse event; D = day; ECG = electrocardiogram; PK = pharmacokinetic; SAE = serious adverse event.

1 Evaluations scheduled for Day 5 in Period 4 will also be performed for participants who discontinue early.

CONFIDENTIAL

209713

10.2. Appendix 2: Study Phases and Treatment Emergent Adverse Events

10.2.1. Study States for Lab, Electrocardiograms, and Vital Signs

Assessments and events will be classified according to the time of occurrence relative to study treatment start date(/time) and stop date(/time).

Study Phase	Definition
Pre-Treatment	Date and Time \leq Study Treatment Start Date and Time
On-Treatment	Study Treatment Start Date and Time $<$ Date and Time \leq Study Treatment Stop Date and Time + 5 days the Date and Time of Early Withdrawal Visit whichever is later.
Post-Treatment	Date and Time $>$ Study Treatment Stop Date and Time + 5 days or the Date and Time of Early Withdrawal Visit whichever is later

10.2.1.1. Study Phases for Concomitant Medication

Study Phase	Definition
Prior	If medication end date is not missing and is before Day -1
Concomitant	Any medication that is not a prior

NOTES:

- Please refer to [Appendix 5: Reporting Standards for Missing Data](#) for handling of missing and partial dates for concomitant medication. Use the rules in this table if concomitant medication date is completely missing.

10.2.2. Treatment Emergent Flag for Adverse Events

Flag	Definition
Treatment Emergent	
 • If AE onset date and time is on or after treatment start date and time & on or before treatment stop date and time + 5 days. • Study Treatment Start Date and Time \leq AE Start Date and Time \leq Study Treatment Stop Date and Time + 5 days. • If the AE onset date is completely missing, the AE is considered as treatment emergent.

NOTES:

- If the study treatment stop date is missing, then the AE will be considered to be On-Treatment.
- Please refer to [Appendix 5: Reporting Standards for Missing Data](#) for handling of missing and partial dates for adverse events. Use the rules in this table if the adverse event onset date is completely missing.

CONFIDENTIAL

209713

10.3. Appendix 3: Data Display Standards & Handling Conventions

10.3.1. Reporting Process

Software	

 The currently supported versions of SAS software (9.4) will be used. 	
Reporting Area	
HARP Server	\\us1salx00259.corpnet2.com
HARP Compound	GSK3640254
Analysis Datasets	

 Analysis datasets will be created according to CDISC standards (SDTM IG Version 3.2 & ADaM IG Version 1.1). For creation of ADaM datasets (ADC1/ADCM/ADAE), the same version of dictionary datasets will be implemented as those being used for conversion from SI to SDTM. 	
Generation of RTF Files	

 RTF files will be generated for all reporting efforts described in the RAP. 	

10.3.2. Reporting Standards

General

 The current GSK Integrated Data Standards Library (IDSL) will be applied for reporting, unless otherwise stated (IDSL Standards Location: https://spope.gsk.com/sites/IDSLLibrary/SitePages/Home.aspx): 
 4.03 to 4.23: General Principles 5.01 to 5.08: Principles Related to Data Listings 6.01 to 6.11: Principles Related to Summary Tables 7.01 to 7.13: Principles Related to Graphics Do not include participant level listings in the main body of the GSK CSR. All participant level listings should be located in the modular appendices as ICH or non-ICH listings.
Formats

 All data will be reported according to the actual treatment the participant received unless otherwise stated. GSK IDSL Statistical Principles (5.03 & 6.06.3) for decimal places (DP's) will be adopted for reporting of data based on the raw data collected, unless otherwise stated. Numeric data will be reported at the precision collected on the eCRF. The reported precision from non eCRF sources will follow the IDSL statistical principles but may be adjusted to a clinically interpretable number of DP's.
Planned and Actual Time

 Reporting for tables, figures, and formal statistical analyses: 
 Planned time relative to dosing will be used in figures, summaries, statistical analyses and calculation of any derived parameters, unless otherwise stated. The impact of any major deviation from the planned assessment times and/or scheduled visit days on the analyses and interpretation of the results will be assessed as appropriate. Reporting for Data Listings: 
 Planned and actual time relative to study drug dosing will be shown in listings (Refer to IDSL Statistical Principle 5.05.1).

CONFIDENTIAL

209713

 • Unscheduled or unplanned readings will be presented within the participant's listings. • Visits outside the protocol defined time-windows (i.e. recorded as protocol deviations) will be included in listings but omitted from figures (mean figures only for PK concentrations), summaries, and statistical analyses (excluding statistical analyses of PK parameters). 	
Unscheduled Visits	

 • Unscheduled visits will not be included in summary tables except for determining the worst-case values. • Unscheduled visits will not be included in figures. • All unscheduled visits will be included in listings. 	
Descriptive Summary Statistics	
Continuous Data	Refer to IDSL Statistical Principle 6.06.1
Categorical Data	N, n, frequency, %
Graphical Displays	

 • Refer to IDSL Statistical Principals 7.01 to 7.13. 	

10.3.3. Reporting Standards for Pharmacokinetics

Pharmacokinetic Concentration Data	
Descriptive Summary Statistics, Graphical Displays and Listings	
Refer to IDSL PK Display Standards. Refer to IDSL Statistical Principle 6.06.1.
 
For continuous data:
 
 • NQs at the beginning of a participant profile (i.e. before the first incidence of a measurable concentration) are deemed to be zero as it is assumed that in this circumstance no drug is yet measurable in the blood. • For NQs at the end of the participant profile (i.e. after the last incidence of a measurable concentration); 
 • for individual plots and pharmacokinetic analyses these are dropped (set to missing) as they do not provide any useful information (and can erroneously indicate that absolutely no drug is present) • for summary statistics, these are set to 0 (to avoid skewing of the summary statistics) • Individual NQs which fall between two measurable concentrations are set to missing (individual values of this nature are assumed to be an anomaly) 
If two or more NQ values occur in succession between measurable concentrations, the profile will be deemed to have terminated at the last measurable concentration prior to these NQs. For the purpose of individual participant plots, these NQs will be set to 0, and the subsequent measurable concentrations will be retained. For the derivation of pharmacokinetic parameters, these NQs and any subsequent measurable concentrations will be omitted (set to missing).
 
Note: Concentration values will be imputed as per GUI_51487 for descriptive summary statistics/analysis and summarized graphical displays only.

Pharmacokinetic Parameter Data	
Descriptive Summary Statistics, Graphical Displays and Listings	
N, n, arithmetic mean, 90% CI of arithmetic mean, geometric mean, 95% CI of geometric mean, SD, SD of logged data CV (%), and between-subject geometric coefficient of variation (CV_b (%)) will be reported.
 $CV_b (\%) = \sqrt{(\exp(SD^2) - 1) * 100}$ 
(SD = SD of Ln-Transformed data)

CONFIDENTIAL

209713

Parameters Not Being Ln-Transformed	Tmax, tlag, λz , λz lower, λz upper, and λz no. of points.
Parameters Not Being Summarized	λz , λz lower, λz upper, and λz no. of points.
Listings	Include the first point, last point and number of points used in the determination of λz and Rsq_adjusted for listings.

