	
 • Analysis will be performed to compare the relative BA of a tablet formulation of GSK3640254 with the capsule formulation, as appropriate. Analyses will be performed on the natural logarithms of AUC(0-∞), AUC(0-t), and Cmax using linear mixed-effect models with treatment, period, and sequence as fixed effects and participant as a random effect. Effects will be estimated, and CIs will be constructed for the following treatment comparison: 
 • Treatment B (test) versus Treatment A (reference) 
Point estimates and 90% CIs for treatment differences on the log scale derived from the model will be exponentiated to obtain estimates for geometric mean ratios and CIs on the original scale.
 • The effect of food (moderate or high fat meal) on the PK of the tablet formulation of GSK3640254 will be similarly analyzed for the following treatment comparisons: 
 • Treatment B (test) versus Treatment C (reference) • Treatment D (test) versus Treatment C (reference) • Non-parametric analysis will be performed to compare the Tmax of a tablet formulation of GSK3640254 with the capsule formulation, as appropriate. The Hodges-Lehmann estimate will be used to produce the median, median difference, and 90% CIs for the following comparison: 
 • Treatment B (test) versus Treatment A (reference) 
A p-value will be generated by the Wilcoxon signed-rank test
 • The effect of food (moderate or high fat meal) on the Tmax of the tablet formulation of GSK3640254 will be similarly analyzed for the following comparisons: 
 • Treatment B (test) versus Treatment C (reference) • Treatment D (test) versus Treatment C (reference) • Summary statistics (arithmetic mean, geometric mean, median, standard deviation, minimum, maximum, and coefficient of variation) for plasma GSK3640254 primary PK parameter values will be summarized by treatment.
Secondary	
 • Based on the individual concentration-actual time data the following secondary plasma PK parameters will be estimated: 
 • tlag, t1/2, CL/F, and Vz/F • Summary statistics (arithmetic mean, geometric mean, median, standard deviation, minimum, maximum, and coefficient of variation) for plasma GSK3640254 secondary PK parameter values will be summarized by treatment.

Endpoint	Statistical Analysis Methods

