2.1. Changes to the Protocol Defined Statistical Analysis Plan

Changes from the originally planned statistical analysis specified in the protocol are outlined in [Table 1](#).

Table 1 Changes to Protocol Defined Analysis Plan

Protocol	Reporting & Analysis Plan	
Statistical Analysis Plan	Statistical Analysis Plan	Rationale for Changes

 None 	
 Randomized population is defined as all participants who were randomly assigned to a treatment sequence 	
 This is a randomized study and listing of randomization schedule will be produced based on randomized population.

 Pharmacokinetic concentration population will be used for the PK concentration listings, summary tables, and plotting of concentration-time data. 	
 Pharmacokinetic concentration population will be used for the PK concentration listings and summary tables. 	
 Study terminated earlier due to potential contamination issue. An abbreviated clinical study report will be reported, and PK figures are not needed.

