3. PLANNED ANALYSES

3.1. Final Analyses

The final planned primary analyses will be performed after the completion of the following sequential steps:

1. All participants have completed the study as defined in the protocol.
2. All required database cleaning activities have been completed and final database release (DBR) and database freeze (DBF) have been declared by Data Management.

The study early terminated due to potential contamination issue in study drug. All participants completed Treatment Period 2 before the study was terminated.

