10.9.7. Pharmacokinetic Tables

Pharmacokinetic: Tables					
No.	Population	IDSL / Example Shell	Title	Programming Notes	Deliverable [Priority]
PK Concentration Data					
3.1.	PK Concentration	PKCT1	Summary of GSK3640254 Plasma Pharmacokinetic Concentration-Time Data (ng/mL) by Treatment		SAC
PK Derived Parameters					
3.2.	PK Parameter	PKPT4	Summary Statistics of Derived GSK3640254 Plasma Pharmacokinetic Parameters (Non-Transformed) Based on Actual Time by Treatment	Parameters with units; present PK parameters in ug/mL or ug.h/mL	SAC
3.3.	PK Parameter	PKPT4	Summary Statistics of Derived GSK3640254 Plasma Pharmacokinetic Parameters (Ln-Transformed) Based on Actual Time by Treatment	Parameters with units; present PK parameters in ug/mL or ug.h/mL	SAC
PK Analysis Tables					
3.4.	PK Parameter	PKPT3	Statistical Analysis of GSK3640254 Plasma Pharmacokinetic Parameters: Analysis of Variance (ANOVA)- Relative Bioavailability	AUC(0-∞), AUC(0-t) and Cmax,	SAC
3.5.	PK Parameter	PKPT3	Statistical Analysis of GSK3640254 Plasma Pharmacokinetic Parameters: Analysis of Variance (ANOVA)- Food Effect	AUC(0-∞), AUC(0-t) and Cmax,	SAC
3.6.	PK Parameter	PKPT3	Statistical Analysis of GSK3640254 Plasma Pharmacokinetic Parameters: Non-parametric analysis- Relative Bioavailability	Tmax	SAC
3.7.	PK Parameter	PKPT3	Statistical Analysis of GSK3640254 Plasma Pharmacokinetic Parameters: Non-parametric analysis-Food Effect	Tmax	SAC

CONFIDENTIAL

209713

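### Do the SAP's two lists of summary statistics for the PK parameter tables conflict in a way that needs a change?

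*SAP*

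**What the plan says.** Three places list the descriptive statistics for the PK parameters.

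- **Protocol 9.4.1** gives the shortest list: "Summary statistics (arithmetic mean, geometric mean, median, standard deviation, minimum, maximum, and coefficient of variation) for plasma GSK3640254 primary PK parameter values". The secondary parameters get the same seven statistics. There is no confidence interval and no between-subject CV (CVb).
- **SAP 7.1.4** (AUC(0-∞), AUC(0-t), Cmax, Tmax) keeps those seven, adds CVb, and ends "and 90% confidence interval (CI) for plasma GSK3640254 PK parameter values will be summarized by treatment". **SAP 7.2.4** (tlag, t1/2, CL/F, Vz/F) does the same: "and 90% CI) for secondary plasma PK parameters of GSK3640254 will be summarized by treatment". Neither says which mean the interval belongs to.
- **SAP 10.3.3**, under the heading for parameter data, asks for N, n, "90% CI of arithmetic mean, geometric mean, 95% CI of geometric mean, SD", and then SD of logged data, CV and CVb. It computes CVb from the SD of ln-transformed values. A separate row headed "Parameters Not Being Ln-Transformed" names Tmax and tlag, along with the λz items.

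The output is two tables in SAP 10.9.7: Table 3.2 for non-transformed parameters, and Table 3.3, whose title ends "Plasma Pharmacokinetic Parameters (Ln-Transformed) Based on Actual Time by Treatment". SAP 2.1 says "Changes from the originally planned statistical analysis specified in the protocol are outlined in" its Table 1, and that table does not mention these statistics.

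**The concern.** Two sections of one plan describe the same tables and do not agree item by item, and nothing says which governs. Three consequences seem possible.

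1. One programmer might print a 90% interval for the geometric mean and another a 95% interval.
2. A programmer who used 10.3.3 alone would print no median or range. That matters most for Tmax, a primary endpoint that is compared through medians.
3. A geometric mean and CVb are requested for Tmax and tlag, yet both are excluded from ln-transformation. A tlag of zero has no logarithm.

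The intervals, CVb and SD of logged data are also additions to the protocol's list that SAP Table 1 does not record. At stake is whether the descriptive PK tables can be produced in only one way.

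**Working it through.** **Side-by-side comparison.** The plan states no figure for these tables, so there is nothing to reproduce. The check is a comparison of the lists.

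| Item | SAP 7.1.4 and 7.2.4 | SAP 10.3.3, parameter data | Protocol 9.4.1 |
|---|---|---|---|
| Both means, SD, CV | yes | yes | yes |
| Median, minimum, maximum | yes | not listed | yes |
| CVb | yes | yes | no |
| SD of logged data | no | yes | no |
| N and n | not listed | yes | not listed |
| 90% CI | yes, mean not named | arithmetic mean | no |
| 95% CI | no | geometric mean | no |

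**Interval level.** There are two readings of the unnamed 90% interval.

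- If it belongs to the arithmetic mean, it is the interval in 10.3.3, at the same level, and 10.3.3 merely adds one more.
- If it belongs to the geometric mean, the levels differ. Even then, printing both intervals with labels obeys both sections.

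No text shows that the second reading was meant.

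**Median and range.** Nothing in 10.3.3 says that its list is exhaustive or overrides 7.1.4 and 7.2.4, which require these statistics. On the first reading, the combined list is the 10 items of 10.3.3 plus median, minimum and maximum: 10 + 3 = 13 items. It includes all seven of the protocol's statistics. Listing 34 (SAP 10.9.9) also gives the parameters by participant, so the median and range can be recovered. The Tmax median appears again in the analysis under SAP 7.1.4.1, if data suffice.

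**Tmax and tlag.** Four of the 10 items in 10.3.3 need logarithms: geometric mean, its interval, SD of logged data and CVb. The row on untransformed parameters is the specific instruction; the sentences in 7.1.4 and 7.2.4 are general. Reading the specific as limiting the general puts Tmax and tlag in Table 3.2 and not in Table 3.3, which is how 10.9.7 divides the output.

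**Size under the adverse reading.** SAP 3.1 states: "All participants completed Treatment Period 2 before the study was terminated". The number treated is not given. Assume the planned 16, with 4 per sequence (Protocol 9.2.2). Through Period 2, A and B occur only in ABCD and BADC, and C and D only in CDAB and DCBA, so n = 4 + 4 = 8 per treatment.

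The interval is GM × exp(± t·s/√n), with s = √ln(1 + CV²).

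- At n = 8, t is 1.895 (90%) and 2.365 (95%). The ratio is 2.365/1.895 = 1.248.
- At n = 6 (12 participants, 3 per sequence), the ratio is 2.571/2.015 = 1.276.
- The documents give no between-subject CV. At an assumed 30%, s = √ln(1.09) = 0.2936. The half-widths at n = 8 are 1.895 × 0.2936/√8 = 0.197 and 2.365 × 0.2936/√8 = 0.245.

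| Assumed geometric CV, n = 8 | 90% CI, × GM | 95% CI, × GM |
|---|---|---|
| 20% | 0.876 to 1.142 | 0.847 to 1.180 |
| 30% | 0.821 to 1.217 | 0.782 to 1.278 |
| 40% | 0.773 to 1.294 | 0.725 to 1.380 |

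The geometric mean itself is the same in both columns. Because 10.3.3 also prints n and the SD of logged data, a reader can compute either interval from the table.

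**The case for a change.** The best argument for acting is that descriptive tables carry more weight than usual in this study. After two periods no participant has received both B and C. With sequence as a fixed effect, the planned model cannot then separate B versus C from the difference between the sequence pairs. The model analyses are in any case conditional on sufficient data (SAP 7.1.4.1). The by-treatment summaries may therefore be the main evidence on the moderate-fat food effect, and the edit would be cheap: one list, two cross-references and one row in Table 1.

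The design point is correct, but it is not cured by tidying the lists. A reader comparing B with C descriptively would use the geometric means and their spread, and these are identical under either list. Only the width of a by-treatment interval could differ, and its level would be printed beside it.

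Some of the objection stands. The lists are not identical, and the interval in 7.1.4 and 7.2.4 should have named its mean. SAP Table 1 is silent on the added statistics. Leaving the geometric mean of Tmax and tlag out of the log-scale table departs slightly from Protocol 9.4.1. The IDSL principle for continuous data cited in SAP 10.3.2, and the shell PKPT4 for both tables, may settle all of this. Neither is in the documents, so nothing here relies on them.

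**Conclusion.** No change to the plan follows. The sections contain an ambiguity and two lists that do not match, which is a drafting slip; a clash of interval levels is not shown. An analyst can settle it from the existing text by printing the union of the lists, labelling each interval with its mean and level, and keeping log-based statistics to the ln-transformed parameters.

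The effect is confined to descriptive Tables 3.2 and 3.3 of an abbreviated report. The 90% intervals for the geometric mean ratios are set in SAP 7.1.4.1 and agree with Protocol 9.4.1; neither they nor the Tmax comparisons change. The most that could vary is the width of the geometric mean interval, by a factor of 1.25 on the log scale at n = 8 or 1.28 at n = 6. That requires the reading which the text does not establish, and it rests on the planned allocation because the actual number treated is not stated. Aligning the lists would make the SAP neater but would make no result or conclusion sounder.
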